9.3. Schedule of Events

Clinical data will be collected at the Baseline 3 month, 6 month, 12 month, and exit visits. In addition if applicable, clinical data will be collected with an exit or death, as well as unscheduled visits. Device data will be collected from device interrogations on Medtronic devices received during the period between the enrollment and exit until study closure; for non-Medtronic devices, device data will not be collected. Data will be collected using eCRFs using an electronic data management system for clinical studies. In addition to eCRF data, non-eCRF data will be collected including device interrogation files (for Medtronic implanted devices only). Surveys may also be used throughout the study.

Data will be stored in a secure, password-protected database, which will be backed up nightly. Data will be reviewed using programmed and manual data checks. Data queries will be made available to study sites for resolution. Study management reports will be generated by Medtronic to monitor data quality and study progress. At the end of the study, the data will be frozen and retained indefinitely by Medtronic. Data Collection requirements are summarized in the table 2 below.

Table 2 Data Collection and study procedure requirements at subject visit

Study Procedure	Baseline	3 month visit	6 month visit	12 month visit	Study Exit
Patient informed consent	X				
Eligibility Verification (Inclusion/ exclusion assessment)	X				
Subject Demographics	X				
Acute MI information	X				
Medical History	X				
Cardiovascular Medications	X	X			
LVEF measurement	X	X*	X (collect if performed as per SOC)	X (collect if performed as per SOC)	
ECG	X	X (collect if performed as per SOC)	X (collect if performed as per SOC)	X (collect if performed as per SOC)	
Referral Status		X	X	X	X
Implant Status (if applicable)		X (if subject receives or has received device implant)	X (if subject receives or has received device implant)	X (if subject receives or has received device implant)	X (if subject receives or has received device implant)
Device Interrogation File (pdd) or CareLink Transmission for subjects implanted with Medtronic device only		X	X	X	X
Adverse Event	As they occur				
System Modification					
Study Deviation					
Subject Death					

* The LVEF measurement needs to be performed ≥ 40 days post-acute MI for MI subjects without revascularization, or ≥ 90 days post-revascularization for post-MI subjects with revascularization done.

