9.6.1. Information Collected

The following information is required to be collected at follow-up visits:

- Referral status
- Implant status
- Cardiovascular Medication categories as listed under Enrollment/ Baseline (for 3-month visit only)

- LVEF measurement as per standard practice.
 - For 3-month visit, the LVEF measurement needs to be performed ≥ 40 days post-acute MI for MI subjects without revascularization, or ≥ 90 days post-revascularization for post-MI subjects with revascularization done.
- ECG as per standard practice
- Cardiovascular Adverse events, Study Deviations and System Modification.

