Figure 1 Study Flow

***For patient enrollment:** Patients must be enrolled ≤ 30 days post-acute MI and must have an $EF < 50\%$ measured ≤ 14 days post-acute MI.

****Referral Criteria:** sustained VT, cardiac or unexplained syncope, clinically significant palpitations, new onset bundle branch block, conduction abnormalities, or symptomatic bradycardia.

Table 1 below specifies the time windows for the required subject visits, which are based on days post-acute MI. If a subject visit falls outside the pre-specified window, a study deviation will be reported, and the original follow-up schedule maintained for subsequent visits.

Data analyses will include follow-up visits, regardless of whether the visits occur within the time window. If a subject has an out of window visit, referral will be counted at the consecutive visit, while non-referral will be counted at the previous visit. For example, if a subject has a 3 months visit at 140 days post MI and is referred, he'll be considered as having been referred at the 6 months visit. On the contrary, if a subject has a 3 months visit at 140 days post MI and is not referred, he'll be considered as not having been referred at the 3 months visit. Rationale of this is:

1. When the late visit does not have the event (e.g. no referral yet), the event also had not happened yet in the window of the previous visit, but it may occur at the consecutive visit.
2. When the late visit has the event (e.g. referral), the status at the next visit is referred, but it is unsure whether the referral would have already happened in the window of the previous visit.

Table 1: Follow-up windows

Study Follow-up Visit	Window (Calculated days post-acute MI)		
	Window Start (days post-MI)	Target (days post-MI)	Window End (days post-MI)
3 month	40	90	120
6 month	150	180	210
12 month	335	365	395

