7.9.1.2 Endpoint definitions

The endpoint will be defined as the clinician's determination to refer the subject for SCD risk stratification and management. The pre-defined reasons for this referral are:

- Subject's LVEF at 3 months determined to be up to 40%

- Subject experiences unexplained syncope, ventricular arrhythmia, AV block, clinically significant palpitations, new onset bundle branch block, conduction abnormalities, or symptomatic bradycardia.

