7.9.1.3 Analysis Methods

Subjects will be evaluated during their three months visit (chronic phase, $\geq 40-90$ days after MI) for determination of the need for SCD risk stratification and management. As of this visit, subjects will be partitioned into several groups: died of cardiovascular causes prior to reaching the 3 months visit, exited or died of non-cardiovascular or unknown causes prior to reaching 3 months visit, reached the 3 months visit and exited because of $\text{LVEF} \geq 50\%$, reached the 3 months visit and had at least one reason for referral for SCD risk stratification and management, reached the 3 months visit and had no reason for referral for SCD risk stratification and management.

Subjects classified as “died of cardiovascular causes” will be all subjects with subject status “death” within the exit CRF and with primary cause of death “non-sudden cardiac death” or “sudden cardiac death” within the death CRF.

Subjects classified as “exited or died of non-cardiovascular or unknown causes” will be all subjects with subject status “death” within the exit CRF and with primary cause of death “non-cardiovascular death” or “unknown classification” within the death CRF and all subjects with subject status “adverse event, lost to follow-up, physician decision, sponsor request or withdrawal by subject” in the exit CRF.

Subjects classified as “reached the 3 months visit and exited because of $\text{LVEF} > 50\%$ ” will be all subjects that will have completed the three months visit and will have subject status “other” within the exit CRF and will have a result of LVEF measurement higher or equal than 50% within the LVEF CRF.

Subjects classified as “reached the 3 months visit and had at least one reason for referral” will be all subjects that will have completed the three months visit and that in the referral CRF will have answer “yes” to the question “does the subject meet referral criteria” and will have at least one reason for referral selected underneath the question “if yes, indicate referral criteria met”.

Subjects classified as “reached the 3 months visit and had no reason for referral” will be all subjects that will have completed the three months visit and that will have answer “no” to the question “does the subject meet referral criteria” in the referral CRF.

Descriptive statistics will be used to summarize these groups and displayed as shown in the example Table 2 below.

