Table 2: Number (%) of subject in each group between enrollment and the 3 months visit

		Enrolled Population
Region 1	Died of cardiovascular causes	XX/XX (XX.XX%)
	Exited or died of non-cardiovascular or unknown causes	XX/XX (XX.XX%)
	Reached the 3 months visit and exited because of LVEF \geq 50%	XX/XX (XX.XX%)
	Reached the 3 months visit and had reasons for referral	XX/XX (XX.XX%)
	Reached the 3 months visit and had no reasons for referral	XX/XX (XX.XX%)
Region 2	Died of cardiovascular causes	XX/XX (XX.XX%)
	Exited or died of non-cardiovascular or unknown causes	XX/XX (XX.XX%)
	Reached the 3 months visit and exited because of LVEF \geq 50%	XX/XX (XX.XX%)
	Reached the 3 months visit and had reasons for referral	XX/XX (XX.XX%)
	Reached the 3 months visit and had no reasons for referral	XX/XX (XX.XX%)
...
Overall	Died of cardiovascular causes	XX/XX (XX.XX%)
	Exited or died of non-cardiovascular or unknown causes	XX/XX (XX.XX%)
	Reached the 3 months visit and exited because of LVEF \geq 50%	XX/XX (XX.XX%)
	Reached the 3 months visit and had reasons for referral	XX/XX (XX.XX%)
	Reached the 3 months visit and had no reasons for referral	XX/XX (XX.XX%)

The same summary statistics will be computed at the 6 months and at the 12 months visits and displayed in tables similar to Table 1, except for the group “exited because of LVEF \geq 50%” as patients are exited from the study for this reason at the 3 months visit only.

Note that at the three months visit, subjects with a LVEF \geq 50% will be exited from the study regardless of other reasons for referral. The proportion of those subjects that had a reason for referral other than LVEF will be computed by region and overall.

Among the subjects with a reason for referral during their three months visit, the proportions and Wilson score 95% CI of those who were referred for sudden cardiac death risk (SCD) stratification and management will be computed.

The subjects with a reason for referral (denominator) will be all subjects that at the three months visit will have at least one referral criterion met in the referral CRF. The subjects referred (numerator) will be

all subjects that will have completed the three months visit and that will have answer “yes” to the question “has the subject been referred or invited for SCD risk stratification” in the referral CRF.

An example SAS code for the computation of the proportions for each region is provided below:

```
proc freq data = referral;
  by region;

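### The documents disagree on when a revascularised subject's 3-month LVEF counts, and the SAP's primary analysis applies no LVEF-timing check, so deferral and non-referral can be mixed

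*SAP*

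**What the plan says.** **Minimum delay.** Protocol 9.6.1 sets two conditions. The first is "For 3-month visit, the LVEF measurement needs to be performed ≥ 40 days post-acute MI for MI subjects without revascularization". The second, for the others, is at least "90 days post-revascularization for post-MI subjects with revascularization done". The footnote to Protocol Table 2 (9.3) repeats both.

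**Visit window.** Protocol Table 3 (9.6) and SAP Table 1 (5.1) give one 3-month window for all subjects: days 40 to 120, target 90, counted from the MI and not from revascularisation.

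**Chronic phase.** Protocol 5.2.2, 12.2.3 and 12.3.5.2 and SAP 7.9.1.3 and 7.9.6.2 place the chronic phase at 40-90 days after MI, whether or not the subject was revascularised.

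**Exit.** Protocol 9.6 and 9.7 exit a subject whose LVEF is 50% or more at the 3-month visit, with no condition on the timing of that LVEF.

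**SAP analysis rules.**
- The LVEF reason (7.9.1.2) is "Subject's LVEF at 3 months determined to be up to 40" per cent, with no minimum delay.
- The primary denominator (7.9.1.3) is "all subjects that at the three months visit will have at least one referral criterion met in the referral CRF".
- The exit group (7.9.1.3) consists of exited subjects who "will have a result of LVEF measurement higher or equal than 50% within the LVEF CRF".
- The re-assessment (6.2) uses the observed proportion with a reason at the 3-month visit.
- On visit timing, SAP 5.1 says "Data analyses will include follow-up visits, regardless of whether the visits occur within the time window". Its reallocation rule deals only with visits outside the window.

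**The concern.** The primary result is the proportion referred among subjects with a reason for referral. Take a subject who has PCI on day 0, a 3-month visit on day 60 and an LVEF of 38%. The visit is in window and in the chronic phase, but the LVEF comes before the delay in Protocol 9.6.1. If the investigator marks the LVEF criterion as met and waits for a later reading before referring, the SAP counts a subject with a reason who was not referred. A decision to wait that is consistent with one part of the protocol is then indistinguishable from a failure to refer.

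Only revascularised subjects can fall into this gap. That exposes the PCI versus non-PCI comparison (a subgroup in Protocol 12.6 and a candidate factor in SAP 7.9.1.3). It also exposes the comparison of regions, if regions differ in how early they see patients or in how many are revascularised. The same readings enter the re-assessment of enrolment, and the LVEF-change endpoint has the same timing conflict.

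**Working it through.** Here an early LVEF means one taken before the delay in Protocol 9.3 and 9.6.1. The term does not imply that this delay is the right one.

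**1. Overlap of the rules.** For revascularisation on day d after the MI, the first day that meets the delay is 90 + d.
- With d = 0, an LVEF on days 40 to 89 is in window but early. That is 50 of the 81 window days (62%).
- With d = 0, the delay and the 40-90 day chronic phase are both met on day 90 only. With d > 0 they are never both met.
- With d > 30, 90 + d exceeds 120, so no day in the window meets the delay.

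**2. The plan's sample size.** Inputs from SAP 6.1: referral proportion 0.70, two-sided 95% Wilson interval, half-width 0.125, at least 80% probability, 30% with a reason, 10% loss by 3 months. The half-width is z·sqrt(p(1−p)/n + z²/(4n²)) / (1 + z²/n). Summing exact binomial probabilities over the outcomes with half-width at most 0.125 gives 0.784 at n = 53 and 0.897 at n = 54. Then 54/0.30 = 180 and 180/0.90 = 200. The plan's figures reproduce. The problem is one of definition, not arithmetic.

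**3. Effect on the primary proportion.** Let f be the share of the denominator present only because of an early LVEF, and q the proportion of them referred. The observed proportion is (1 − f)·0.70 + f·q. The documents give neither f nor q, so both are assumptions.

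| f | q = 0.40 | q = 0.70 | q = 0.90 |
|---|---|---|---|
| 10% | 67% | 70% | 72% |
| 20% | 64% | 70% | 74% |
| 30% | 61% | 70% | 76% |
| 45% | 56.5% | 70% | 79% |

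For f = 20%: 0.8 × 70 + 0.2 × 40 = 64, and 0.8 × 70 + 0.2 × 90 = 74. The sign depends entirely on whether q is below or above 0.70. In this grid the shift exceeds the planned half-width of 12.5 points only at f = 45% with q = 0.40 (13.5 points).

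**4. Effect on the re-assessment.** Suppose early LVEFs raise the observed proportion with a reason while 30% have a reason apart from an early LVEF.
- Observed 35%: 54/0.35/0.90 gives 172 enrolled. Then 172 × 0.90 × 0.30 is about 46 subjects, and the probability of a width of 25 points or less is about 0.34.
- Observed 40%: 54/0.40/0.90 = 150 enrolled. Then 150 × 0.90 × 0.30 is about 40 subjects, and the probability is about 0.11.

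**5. Cost of leaving early LVEFs out.** With f = 10%, 54 × 0.90 = 48.6, or 49 subjects. At an observed 70% the full width goes from 23.8 to 24.9 points, and the probability of 25 points or less falls from 0.897 to 0.48. Keeping 54 would need 54/(0.30 × 0.90)/0.90 = 222.2, so 223 enrolled per region. With f = 25%, n is 40, the width 27.4 points, the probability 0.11 and the enrolment 267.

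**The case against.** The strongest reply is that the SAP follows the protocol's own primary analysis section. Protocol 12.2.3 assesses reasons for referral in a chronic phase of 40-90 days for all subjects, and a day-60 LVEF lies inside it. A reader might infer that the SAP has dropped a settled 90-day rule and that the primary denominator should be restricted to it. The documents do not support that, because they contain both rules and do not rank them.

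Three further points stand.
- The denominator does not take in every recorded LVEF. It rests on the investigator's answer in the referral CRF plus a selected criterion. An investigator who is waiting for a later LVEF may answer no, and that subject is then not in the denominator.
- The exit row describes subjects who actually left under a protocol rule without a timing condition. Moving them would misstate disposition and recover no data.
- Deferral is partly visible elsewhere: reasons for non-referral in Table 8 (SAP 7.9.5.3), possible 6- and 12-month referral tables (7.9.1.3), the time-to-referral curve (7.9.3.3), and any reported deviation from the LVEF timing (7.1.2).

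None of these separates deferral from non-referral in Table 3. Nothing in the SAP tells the analyst which 3-month LVEFs were early, and the single window allows them without a visit deviation.

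**Conclusion.** The contradiction is in the text, and it reaches the primary proportion, the count with a reason for referral and the re-assessment. For revascularised subjects, Table 3 can mix deferral with non-referral, and the regional and PCI versus non-PCI comparisons are exposed.

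The size cannot be fixed from the documents. They give no revascularised share, no share of early LVEFs and no referral rate after an early LVEF. At an assumed 20% of the denominator, the shift from a true 70% is 6 points down to 4 points up for referral rates of 40% to 90%. These figures concern only subjects whose sole reason is an early LVEF. Subjects with syncope, arrhythmia, conduction or another non-LVEF reason stay in the denominator whatever the LVEF timing, and the plan's 30% covers all reasons.

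A reader might infer that the referral proportion must be biased downward, or that regions seeing patients early will look worse. Either would require referral after an early LVEF to be less frequent than 70%, and nothing in the documents establishes that.

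**What to change.** - **Protocol.** Reconcile the LVEF timing in 9.3 and 9.6.1 with the visit window (Protocol Table 3, SAP Table 1), the exit rule (9.6, 9.7), the 40-90 day chronic phase (5.2.2, 12.2.3) and the LVEF-change endpoint (12.3.5.2, SAP 7.9.6.2). Which timing should hold is for the sponsor to settle.
- **SAP 7.9.1.3.** Derive an LVEF-timing flag from the LVEF, MI and revascularisation dates.
- **Table 3.** Report it for all subjects with a reason, and again without those whose only reason is an LVEF earlier than the protocol's delay.
- **Table 2.** Within the reason-for-referral row and the LVEF 50%-or-more exit row, show how many LVEFs were early. Do not reclassify actual exits.
- **SAP 6.2.** Compute the proportion with a reason both ways before changing enrolment.

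The cost is some SAP wording, one derived variable and one further version of a table. The restricted analysis has a smaller denominator and a wider interval, and 54 subjects leave almost no slack. Revascularisation dates must also be available in the CRFs. Protocol Table 2 collects acute MI information and medical history at baseline but lists no revascularisation item at follow-up, and the CRFs are held separately, so this has to be checked first.

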  table referred/binomial (cl = wilson) alpha = 0.05 out = perc;
  ods output binomialCLs=percConf;
run;
```

The results will be shown for each region and overall in a table similar to the example table below:

Table 3: percentage (95% CI) of subjects referred for sudden cardiac death risk (SCD) stratification and management, among the subjects with at least one reason for referral at the 3 months visit (chronic phase)

Region	Proportion Referred	95% CI
Region 1	XX/XX (XX.XX%)	(XX.XX% - XX.XX%)
Region 2	XX/XX (XX.XX%)	(XX.XX% - XX.XX%)
...
Overall	XX/XX (XX.XX%)	(XX.XX% - XX.XX%)

A subject not referred for SCD risk stratification and management during their three months visit may later be referred. Thus, similar descriptive statistics may be generated at the 6 and at the 12 months post-baseline visits and displayed in a table similar to table 2 above.

Further, as part of an attempt to continually train the physicians on referring subjects with a reason for referral, periodic feedbacks on referral rates will be provided. Whether these periodic feedbacks will have an impact on referral rate will be investigated by producing, for each region and overall and over time, a penalized B spline plot. A SAS code similar to the below will be used:

```
ods graphics on / attrpriority=none;
proc sgplot data=referral noautolegend;
  title 'Penalized B-Spline for each region';
  styleatrrs datalinepatterns=(solid);
  pbspline y=prop x=time/group=region;
run;
```

Additional analyses may be provided and described in the final report.

Additionally to the analyses described above, logistic regression models might be used overall and by region, to estimate the odds ratios of referring patients for SCD stratification and management

depending on different factors, such as age, gender, LVEF≤40% versus any other reason for referral, physician's specialty, PCI versus non-PCI patients, STEMI versus non-STEMI patients. An example SAS code similar to the below will be used:

```
proc logistic data = referral;
  by region;
  class factor/descending;
  model referred (event = '1') = factor/expb;
  oddsratio factor;
  ods output ParameterEstimates = ParEstim;
  ods output OddsRatiosWald = OREstim;
run;
```

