where referred is the outcome and is equal to 1 if the subject has been referred and 0 otherwise, factor is the independent factor of interest (eg: reason for referral, physician's specialty). Results of the logistic regression model will be displayed by means of either tables or plots.

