It may also happen that a patient might have an SCD risk stratification visit without having been referred, for example, patients who had an SCD risk stratification visit for secondary prevention. An additional table will then be created to show, for each visit, the number of subjects that were not referred but had an SCD risk stratification visit and among those, the proportion of subjects that had a reason for referral.

Second, the proportion and Wilson score 95% CI of subjects recommended for ICD/CRT-D at the three months visit, at the 6 months and at the 12 months visits will be computed overall and by region, for the Enrolled Population and for the subjects in the numerator in table 3 above, that is, all subjects that have had an SCD risk stratification visit (called in table 4 below “SCD risk stratification Population””).

A SAS code similar to the example SAS code shown in Section 7.9.1.3 will be used. For each follow up visit, the results will be shown in a table similar to Table 5 below.

Table 5: Proportion (95% CI) of subjects indicated to receive ICD/CRT-D, at visit X

Region	Enrolled Population		SCD risk stratification population	
	n/N (%)	95% CI	n/N (%)	95% CI
Region 1	XX/XX (XX.XX%)	(XX.XX% - XX.XX%)	XX/XX (XX.XX%)	(XX.XX% - XX.XX%)
...
Overall	XX/XX (XX.XX%)	(XX.XX% - XX.XX%)	XX/XX (XX.XX%)	(XX.XX% - XX.XX%)

Where n is number of the subjects “recommended for ICD/CRT-D” and N is either the Enrolled Population or the SCD risk stratification population.

In addition to the above analyses, logistic regression models similar to the example model in Section 7.9.1.3 might be fitted overall and by region, to estimate the odds ratios of being indicated for an ICD/CRT-D, depending on different factors, such as sex, age, specialty of physician who performed the ICD/CRT-D risk stratification, type of device received – ICD or CRT-D, PCI versus non-PCI patients, STEMI versus non-STEMI patients . Results will be displayed either by means of either tables or of plots.

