7.9.4.3 Analysis methods

At each follow-up visit, the cumulative proportion of subjects who experienced cardiovascular mortality between each visit will be computed. A SAS code similar to the example SAS code shown in Section 7.9.1.3 will be used and the results will be shown in a table similar to Table 7 below.

Table 7: Proportion of post-acute MI patients who experienced cardiovascular mortality

Region	3 months visit	6 months visit	12 months visit
China	XX/XX (XX.XX%)	XX/XX (XX.XX%)	XX/XX (XX.XX%)
Taiwan	XX/XX (XX.XX%)	XX/XX (XX.XX%)	XX/XX (XX.XX%)
India	XX/XX (XX.XX%)	XX/XX (XX.XX%)	XX/XX (XX.XX%)
Korea	XX/XX (XX.XX%)	XX/XX (XX.XX%)	XX/XX (XX.XX%)
South East Asia	XX/XX (XX.XX%)	XX/XX (XX.XX%)	XX/XX (XX.XX%)
Middle East, Africa, Central Asia and Turkey	XX/XX (XX.XX%)	XX/XX (XX.XX%)	XX/XX (XX.XX%)
Overall	XX/XX (XX.XX%)	XX/XX (XX.XX%)	XX/XX (XX.XX%)

Further, for subjects who experience cardiovascular mortality, a subject's time to death will be computed in months from enrollment to date of death. If a subject does not meet the endpoint, the subject will be censored at the later of their last follow-up visit or exit. A competing risks event curve will be generated with accompanying 95% confidence bounds and non-cardiovascular mortality accounted for. A SAS code similar to the example code below will be used.

```
proc lifetest data=KM plots=cif(test) timelist=0 1 2 3 4 5 6 7 8 9 10 11 12;
  by region;
  time T*Status(0) /eventcode=1;
run;
```

where T will be the time in months from enrollment to date of cardiovascular death and Status will be an indicator variable with 3 values: 0 for censored observations, 1 for patients who died for cardiovascular death and 2 for subjects who died for non-cardiovascular death. Results will be determined separately for each region and overall.

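### The example SAS code for the primary Wilson interval names no event level, so run as written it returns the interval for subjects who were not referred (Table 3, and Tables 5 and 6 where the code is reused)

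*SAP*

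**What the plan says.** SAP Section 7.9.1.3 states the target in prose: among subjects with a reason for referral at the three-month visit, "the proportions and Wilson score 95% CI of those who were referred for sudden cardiac death risk (SCD) stratification and management will be computed". Table 3 reports this as the proportion referred, with a 95% CI, by region and overall.

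The example code that follows opens with "proc freq data = referral", runs by region, and requests "table referred/binomial (cl = wilson) alpha = 0.05 out = perc". The limits are exported by "ods output binomialCLs=percConf". There is no LEVEL= option inside BINOMIAL and no ORDER= option on the PROC FREQ statement.

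Later in the same section, beside the logistic model on the same dataset, the coding is given: "where referred is the outcome and is equal to 1 if the subject has been referred and 0 otherwise". That logistic code does name the event: "model referred (event = '1') = factor/expb".

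The PROC FREQ example is carried forward. Section 7.9.2.3 (Table 5) says "A SAS code similar to the example SAS code shown in Section 7.9.1.3 will be used", and Section 7.9.3.3 (Table 6) uses the same sentence. Section 7.9.4.3 (Table 7) says "A SAS code similar to the example SAS code shown in Section 7.9.1.3 will be used and the results" will go into its table. The shells of Tables 5 and 6 have 95% CI columns. The shell of Table 7 has only n/N and a percentage.

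**The concern.** PROC FREQ computes the binomial proportion and its limits for one level of the variable. If no level is named, it takes the first in sort order. With 0/1 coding that is 0, the subjects not referred. A No/Yes coding gives the same result, because No sorts before Yes.

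The study tests no hypothesis for this objective, and the sample size was set on the width of this interval. It is therefore the main inferential result of the primary objective. If the example were run as printed, Table 3 would set a correctly read proportion referred beside the interval for its complement. The same would happen in Tables 5 and 6, where the outcomes (indicated for a device, received a device) may be uncommon and the two intervals would lie near opposite ends of the scale.

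**Working it through.** **Inputs.** From SAP 6.1: assumed proportion referred 0.70, half-width 0.125, 30% with a reason for referral, 10% drop-out and death to three months. From SAP 7.2: two-sided 95% intervals, so z = 1.96. From SAP 7.9.1.3: the code and coding above. From outside the documents: the default level used by PROC FREQ.

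**Wilson interval for x of n**, with p = x/n:
- centre = (p + z²/2n) / (1 + z²/n)
- half-width = z·√(p(1−p)/n + z²/4n²) / (1 + z²/n)

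**1. The plan's own figure.** The exact binomial probability that the Wilson half-width is at most 0.125 at p = 0.70 is 0.784 for n = 53 and 0.897 for n = 54. So 54 is the smallest n that reaches 80%. Then 54/0.30 = 180 and 180/0.90 = 200. The SAP's 54, 180 and 200 are reproduced.

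**2. What Table 3 should show at the planning values.** 0.70 × 54 = 37.8, so take 38 referred and 16 not.
- n = 54: z²/n = 0.0711 and z²/2n = 0.0356.
- Referred, p = 38/54 = 0.7037: centre = 0.7393/1.0711 = 0.6902; half-width = 1.96 × √(0.003861 + 0.000329)/1.0711 = 0.1185. Interval **57.2% to 80.9%**.

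**3. What the code as written exports (level 0).**
- Not referred, p = 16/54 = 0.2963: centre = 0.3319/1.0711 = 0.3098; half-width 0.1185. Interval **19.1% to 42.8%**.

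The two intervals do not overlap. Each is 100% minus the other (100 − 80.9 = 19.1; 100 − 57.2 = 42.8) and the half-widths are equal. The width calculation in step 1 is therefore unaffected by which level is analysed.

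**4. What is not reversed.** The OUT= dataset lists the count and percentage of both levels, so 38/54 (70.4%) can be read correctly. Only the limits are for the wrong level.

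**5. Tables 5 and 6, illustration only.** The documents give no expected rate of indication or implant. The rates below are assumptions, on the planned 200 enrolled per region.

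| Assumed events | Intended interval | Interval from the code |
|---|---|---|
| 10/200 (5%) | 2.7% to 9.0% | 91.0% to 97.3% |
| 20/200 (10%) | 6.6% to 14.9% | 85.1% to 93.4% |

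**6. Edge cases by region.** If every subject in a region has the event, level 1 is the only level and the code happens to be right there. If none has it, level 1 is absent, so naming it would leave nothing to compute; the formula at x = 0 gives limits of 0 and z²/(n + z²).

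**The case against.** The strongest reply is that the prose governs and is right. Section 7.9.1.3 defines the numerator as subjects answered yes to having been referred or invited, Table 3 is headed accordingly, and the code is offered only as an example, with similar code elsewhere. Section 10 requires programs for primary-objective tables to be independently programmed or peer reviewed, and a 19% to 43% interval beside a 70% estimate would be hard to miss. All of that stands. It makes this an error in the specification, not evidence that a wrong interval will be reported. It does not make the printed code return what the table labels. Protection is also weaker for Tables 5 and 6, where self-validation is permitted.

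Four stronger readings are tempting and are not supported:
- **The error would go unnoticed near 50%.** At n = 54 the reversed interval does contain the estimate for 24 to 30 referred. At 24/54 (44.4%, an assumed count) it would be 42.4% to 68.0% instead of 32.0% to 57.6%. But the estimate would then sit 2.0 points above one limit and 23.6 below the other, which is visibly lopsided. Closer to 50% the error itself shrinks.
- **Table 7 is also wrong.** It reuses the code, but its shell shows no interval, so its display is unaffected.
- **The interval's meaning would switch between regions in Table 3.** That needs every eligible subject in a region to be referred. At the planning values the probability is 0.7^54, about 4 in a billion. It is conceivable only in small secondary subsets.
- **Precision or sample size is compromised.** Step 1 and the mirror property in step 3 show that neither changes.

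**Conclusion.** The point holds, with limited scope. Run as written, the example code gives the Wilson interval for subjects not referred. This contradicts the SAP's own text and the Table 3 heading, and it is inconsistent with the logistic code for the same variable, which does name the event. At the planning values the limits would be 19.1% to 42.8% where 57.2% to 80.9% is meant. The same reversal would reach the interval columns of Tables 5 and 6 if the code is adapted without change.

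The conclusion rests on two things: the PROC FREQ default for an unnamed level, which the documents do not state but a test run can confirm, and the 0/1 coding, which is stated beside the logistic model but for the same variable and dataset. Estimand, point estimates, interval width and the 54, 180 and 200 are sound. This is a correction to example syntax and does not touch the design.

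**What to change.** In the SAP 7.9.1.3 example, write `table referred / binomial(level='1' cl=wilson) alpha=0.05 out=perc;`, or give the formatted event value if the variable carries a format. In Sections 7.9.2.3 and 7.9.3.3, state the event level (indicated; received a device) where the code is reused for Tables 5 and 6. For a region with no events, state that the Wilson limits are computed from the formula with x = 0.

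The cost is one option in the code and a sentence in each place where it is reused. No change to data collection, sample size or the protocol is needed.
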